Full Study Title: Effect of a Wide Spectrum Nutritional Supplement on Mitochondrial Function in Children with Autism Spectrum Disorder (ASD)

Principal Investigator: [name]; Co-Investigators: [name]

Sponsor: [name]; IND 142751; ClinicalTrials.gov ID: NCT03835117; Protocol Version 02/11/2022

Funding Source: Turnabout for Autism (Private Foundation), Pleasanton CA.

	Synopsis
Protocol Title	Effect of a Wide Spectrum Nutritional Supplement on Mitochondrial Function in Children with Autism Spectrum Disorder (ASD)
IRB	WCG Institutional Review Board
Protocol Ver	Wednesday, August 3, 2022
Sponsor	[name], Rossignol Medical Center, Phoenix AZ
IND # / FDA	IND 142751; FDA Division of Psychiatry; Protocol Version 1.4
NCT ID	NCT03835117
Principal Investigator	[name], PhD, Rossignol Medical Center, [name]
Site- Investigator	[name], Southwestern Autism Resource and Research Center (SARRC), Phoenix AZ
Co-Investigators	1. [name], Director of CNNH NeuroGenomics Program, Center for Neurological and Neurodevelopment Health, Voorhees, NJ. 2. [name] D.O. (SARRC), Phoenix AZ
Clinical Sites	1. SARRC, Phoenix, AZ
Laboratory Sites	1. Laboratory of [name], State University of New York Downstate—[name] 2. Religen Inc, Plymouth Meeting, PA 3. Laboratory of [name], Icahn School of Medicine at Mount Sinai, NY NY 4. Laboratory of [name] at the University of Oklahoma Health Sciences Center in Oklahoma City, OK 5. 3billion Laboratory in Seoul, South Korea 6. Iliad Inc, Plymouth Meeting, PA
Study Design	Prospective Randomized 24-week Double-Blind Placebo-Controlled Cross-over
Objectives	To evaluate the metabolic effects of a comprehensive wide-spectrum supplement for children with ASD to determine whether it physiologically targets mitochondrial pathways known to be abnormal in children with ASD.
Participants	Up to 50 children, aged 2 years 6 months to 17 years 3 months with confirmed ASD and mitochondrial dysfunction. Participants will have moderate disease severity (clinic global impression of 4 or above) and stable behavioral, education and medical treatment. Those with severe intellectual impairment, disruptive behavior or medical conditions such as epilepsy will be excluded.

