Investigational Product	Weight adjusted wide-spectrum oral nutritional supplement powder and gel capsules that targets mitochondrial support produced by NeuroNeeds (Old Lyme, CT) taken in two divided doses vs oral placebos.
Safety	Physical examination, safety labs, Adverse Event Reporting, safety monitoring
Statistical Methods	The primary analysis will be intent-to-treat, defined as all randomized subjects. Mixed-model regression will determine whether blinded treatment produces a greater normalization in mitochondrial function over the 12-week period as compared to placebo treatment over the same time period. Similar analysis will test secondary outcome measures. Assuming a medium effect size of 0.5, the study provides an 80% power assuming a 0.01 alpha (allowing correction for multiple primary end-points). Secondary outcome measures will include the Improvement item of the Clinical Global Impression Scale and behavioral scales such as the Aberrant Behavior Checklist. Multivariable logistic regression will be used to select biomarkers that can significantly predict treatment response.

Full Study Title: Effect of a Wide Spectrum Nutritional Supplement on Mitochondrial Function in Children with Autism Spectrum Disorder (ASD)

Principal Investigator: [name]; Co-Investigators: [name]

Sponsor: [name]; IND 142751; ClinicalTrials.gov ID: NCT03835117; Protocol Version 02/11/2022

Funding Source: Turnabout for Autism (Private Foundation), Pleasanton CA.

Funding	Turnabout for Autism (Private Foundation), Pleasanton CA
---------	--

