#### **4. SPECIFIC AIMS**

**Primary Aim: To determine if a wide-spectrum nutritional supplement can influence**

**mitochondrial activity in 50 individuals with ASD and signs and symptoms of abnormal**

**mitochondrial function.** The trial design will be a 24-week randomized, DBPC cross-over study.

We hypothesize that the supplement will result in a greater ability to normalize mitochondrial activity as compared to placebo. To test this hypothesis we will:

- a. Test mitochondrial activity at baseline and after the placebo and supplement arms of the study and determine if the nutritional supplement normalizes mitochondrial activity significantly more than placebo.
- b. Test redox metabolism at baseline and after the placebo and supplement arms of the study and determine if the nutritional supplement improves redox metabolism significantly more than placebo.
- c. To determine if specific biomarkers (Folate Receptor Autoantibody, Single Nucleotide Polymorphism) can predict response to treatment.

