## 5. RESEARCH PLAN

### Trial Design

50 children with ASD and signs and symptoms of abnormal mitochondrial activity will be randomized in 1:1 ratio to receive a wide-spectrum nutritional supplement that targets mitochondrial function or placebo for 12 weeks under DBPC conditions. Each participant will serve as their own control in the cross-over design. Using a phone screen, we will identify children (age  $\geq$  2:6 and  $<$  17:3) with a diagnosis of ASD and evidence of mitochondrial function which is significantly higher or lower than average (here forth referred to as mitochondrial dysfunction). Children with suspicion of mitochondrial dysfunction will be invited to participate in a screening visit to make sure they meet including and exclusion criteria. If the screening visit is longer than 6 weeks from the prescreening, we will repeat the baseline metabolic testing to ensure an accurate baseline mitochondrial measurement. If they meet criteria, the baseline visit will be completed within 2 week but we will attempt to complete it on the same day (Table 1). Upon successful completion of the baseline visit, the participant will enter Phase 1 of the trial and will be randomized to receive active treatment or placebo for 12 weeks under DBPC conditions. At the end of the 12 weeks (end of Phase 1), the participant will return for evaluations similar to the ones conducted at baseline. Upon successful completion of the post-Phase 1 visit, the participant will start Phase 2 where they will receive active treatment or placebo, depending on what they received during Phase 1 – they will be crossed over to the opposite treatment regimen. Potential AEs, compliance and concomitant treatments will be monitored every four weeks.

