15. Clinical Global Impression for Improvement (CGI-I): The CGI-I is a 7-point measure of overall symptomatic change compared to baseline  that will be used as a **key primary** outcome measure. Scores range from 1 (Very Much Improved) through 4 (Unchanged) to 7 (Very Much Worse). All aspects of the child's condition need to be integrated to assign the CGI-I score. The CGI-I will be rated by an assessor who is blind to treatment assignment, AEs, and medication dose. Both the standard CGI-I and the newly developed CGI-I-ASD will be completed, with the CGI-I completed before the CGI-I-ASD. Ratings of Much Improved or Very Much Improved on the CGI-I will be used to define positive response.

16. Parent Target Problems (PTP): At baseline, parents will be asked to nominate the two most important ASD problems for the child. Through brief discussion, the frequency (for episodic behaviors such as insists on daily routines) or constancy (for problems such as language delay or rigidity reflecting more enduring patterns), intensity and impact of the behavior on the family are established. Responses from this systematic inquiry are documented in a brief narrative. The narrative will be reviewed monthly and a new narrative documented. This review will assist with the scoring of the CGI-I in real time.  At the end of the trial, the narratives will be reviewed by a panel blind to treatment assignment. This method has been shown to be reliable and valid in placebo-controlled studies. 

17. Children's Yale-Brown Obsessive-Compulsive Scales-ASD (CYBOCS-ASD): The CYBOCS-ASD is a modified version of the CYBOCS developed for children with Obsessive-Compulsive Disorder.  The modified version is a semi-structured clinician-rated scale designed to rate the current severity of repetitive behavior in children with ASD (i.e., Time Spent, Interference, Distress, Resistance, and Control). Each item is scored from 0 (least symptomatic) to 4 (most symptomatic), yielding a Total score from 0 to 20. It has established reliability and validity  and is sensitive to change. 

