## **Statistical Analysis**

All data analysis for the primary study aims will be conducted by the principal investigator. The primary analysis will be intent-to-treat, defined as all randomized subjects. Exploratory “per protocol” analysis will be conducted on participants who adhered to protocol. Analyses will be performed with R 3.02 (<http://www.r-project.org>) or SAS 9.3 (SAS Institute, Cary, NC).

Sample Size Justification and Power Analysis: Assuming a medium effect size of 0.5, the study provides an 80% power assuming a 0.01 alpha (allowing correction for multiple primary end-points)..

Primary Hypothesis: After 12 weeks of taking the nutritional supplement will improve mitochondrial function more than taking the placebo for 12 weeks. To test this hypothesis, we will use a mixed model using baseline and all post-randomization measures of mitochondrial activity. To deal with missing post-treatment data, the model will be conditioned on all baseline values. This conditional joint response model is more tolerant of missing data than ANCOVA and is less biased than carrying baseline data forward to endpoint.

Safety analyses: Adverse events (AE) will be systematically monitored using a 34-item form. It includes specific queries about major body systems, activity level, sleep, appetite, and general health. New events, whether presumed related to treatment or not, are classified as AEs and rated as Mild, Moderate or Severe (see details below). The occurrence of an AE will be counted once at the highest level of severity (e.g., a report of mild nausea followed by a report of moderate nausea in the same child would count as an occurrence of moderate nausea). The frequency of AEs by severity will be evaluated using a Fisher’s exact test. We will pursue exploratory analyses such as survival analyses using time to AE as the response variable.

Validation of the CGI-ASD: In addition to the standard CGI-S and CGI-I we will use a new a structured CGI rating scale called the CGI-S-ASD and CGI-I-ASD respectively. We will compare the performance of the standard and new CGI rating scales. Since the CGI-ASD provide guidance for completing the ratings we will have the rater complete the standard scale before the new scale. The correspondence between each scale and other outcome measures will be studied as well as the performance of the scales as outcome measures.

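### Primary Aim c tests biomarkers against a yes/no response, with at most 50 children; models on the full outcome scale would usually keep more power

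*Combined protocol and SAP*

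**What the plan says.** Section 4 (Specific Aims) lists as item c of the Primary Aim: "To determine if specific biomarkers (Folate Receptor Autoantibody, Single Nucleotide Polymorphism) can predict response to treatment". The method appears once, in the Synopsis under Statistical Methods: "Multivariable logistic regression will be used to select biomarkers that can significantly predict treatment response". Section 6 (Statistical Analysis) gives no model, response variable, alpha or power for this aim.

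The only definition of response is in section 5, Developmental Assessments, item 15: "Ratings of Much Improved or Very Much Improved on the CGI-I will be used to define positive response". The same item describes the scale: "The CGI-I is a 7-point measure of overall symptomatic change compared to baseline". No responder threshold is given for mitochondrial function, although item c belongs to the mitochondrial Primary Aim.

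For the treatment effect, section 6 keeps the whole scale: "we will use a mixed model using baseline and all post-randomization measures of mitochondrial activity". The Synopsis promises a similar analysis for the secondary outcomes, CGI-I among them. The sample is stated in the Synopsis as "Up to 50 children, aged 2 years 6 months to 17 years 3 months with confirmed ASD and mitochondrial dysfunction".

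**The concern.** Logistic regression as ordinarily used needs a two-valued outcome. Under the one response rule available, CGI-I scores 1 and 2 become responders and scores 3 to 7 become non-responders. A child one step short of response then counts the same as a child rated very much worse. If response were instead meant in terms of mitochondrial function, someone would have to choose a threshold that the protocol does not contain.

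The plan therefore drops to two categories only for the biomarker question, and no reason is given. A marker truly linked to response would be less likely to be found, and a null result for Aim c would partly reflect the analysis scale. The Potential Benefits text in section 7 hopes that the study may identify subgroups of children who could benefit, so the question matters to the sponsor.

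**Working it through.** **1. The plan's own power figure.** Section 6 states: "Assuming a medium effect size of 0.5, the study provides an 80% power assuming a 0.01 alpha (allowing correction for multiple primary end-points". Section 5 (Trial Design) adds: "Each participant will serve as their own control in the cross-over design". So take a paired t-test with standardised difference 0.5, N = 50 and two-sided alpha 0.01. The noncentrality is 0.5 × √50 = 3.54, and the power is 79.9%. The stated 80% reproduces if all 50 children give paired data. It concerns the treatment comparison only; no power is stated for Aim c.

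**2. Inputs for Aim c.**
- From the protocol: N at most 50, a 7-point CGI-I, and the responder cut at scores 1 and 2.
- Assumed, because the protocol is silent: marker effect, marker prevalence, share of responders, and alpha 0.05 for this aim. The only alpha stated is 0.01, so that is shown too.
- Simplification: one response per child, with the two cross-over periods not modelled.

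**3. Closed-form check.** Take a binary marker splitting the children 25/25, a difference of 0.8 SD and alpha 0.05.
- Full scale, normal approximation: power = Φ(0.8 × √(25/2) − 1.96) = Φ(0.87) = 80.7%.
- Cut with 50% responders overall: the rates are Φ(0.4) = 0.655 and 0.345, a difference of 0.311. Then power = Φ[(0.311 − 1.96 × √(2 × 0.5 × 0.5/25)) / √(2 × 0.655 × 0.345/25)] = Φ(0.034/0.134) = 59.9%.
- With 30% responders the same formula gives 54.1%, and with 20% it gives 45.7%.
- Losses: about 21, 27 and 35 points. This approximation runs somewhat below the simulated logistic likelihood-ratio test, so the simulations below show smaller losses.

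**4. Simulation, binary marker.** N = 50, a difference of 0.9 SD, alpha 0.05. The tests are a t-test on the continuous outcome, a Mann-Whitney test on a well-spread 7-category version, and the logistic likelihood-ratio test on the cut.

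| Marker prevalence | Continuous | 7-point | Logistic, 20% / 35% / 50% responders |
|---|---|---|---|
| 50% | 87–88% | 84% | 58% / 69% / 75% |
| 30% | 81–82% | 76–79% | 56% / 62% / 63% |

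At 0.7 SD, with 30% prevalence and 20% responders, the three powers are 60.2%, 56.0% and 38.1%. Over differences of 0.7 and 0.9 SD, both prevalences and three responder shares, repeated runs give losses of about 13 to 31 points against the continuous outcome. Against the 7-point score they are about 8 to 28 points. Simulation error moves either end by about a point.

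**5. Simulation, continuous marker.** The marker–outcome correlation is 0.385, chosen to give 80% power on the continuous scale at alpha 0.05.

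| Responders | Continuous | 7-point | Logistic | Loss vs continuous | Loss vs 7-point |
|---|---|---|---|---|---|
| 50% | 80.2% | 75.3% | 61.9% | 18 | 13 |
| 30% | 80.2% | 77.1% | 57.1% | 23 | 20 |
| 20% | 80.2% | 77.1% | 50.5% | 30 | 27 |

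At alpha 0.01, with correlation 0.46 (again 80% on the continuous scale), the losses are 24, 30 and 38 points against continuous and 17, 26 and 35 against the 7-point score.

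**6. Where the loss shrinks.**
- Weak marker (0.5 SD): about 7 to 17 points against continuous and 4 to 12 against the 7-point score at alpha 0.05. At alpha 0.01 these fall to about 5 to 9 and 2 to 5, because power is low either way.
- CGI-I ratings falling in only three levels, with 50% responders: about zero.

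**7. Form of the mitochondrial outcome.** Section 5 (Trial Design) enrols children whose function is well above or well below average, and the hypothesis is normalisation. Benefit is a fall for some and a rise for others. In simulations with half the children high and half low, and a 0.7 to 0.9 SD larger move toward normal in marker-positive children, regressing the raw change on the marker had 2 to 5% power, which is no better than chance. Change toward normal had about 68 to 88%. Logistic regression on a normalised yes/no outcome had about 40 to 74%.

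**The case against.** The strongest case against the point has four parts.

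- **The protocol never says that mitochondrial change is dichotomised.** This stands. A reader might infer it because Aim c sits under the mitochondrial Primary Aim and the method is logistic. But the only cut in the text is on CGI-I, so the continuous-scale loss is conditional and must not be attached to CGI-I.
- **The size depends on inputs that nobody has stated.** This also stands. The range covers the settings listed above. For CGI-I it further depends on how ratings spread over the seven levels, and a material loss in every setting cannot be claimed.
- **A simple switch to the raw mitochondrial value could do worse than the planned method.** This stands, as step 7 shows, and it determines the form of the fix.
- **The scope is narrow.** The logistic model appears in one Synopsis sentence, and treatment effects on CGI-I and the other outcomes are not cut. This is true, but that sentence is the only analysis given for an item of the Primary Aim.

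What survives is that the single stated method and the single response rule together discard graded information. Nothing in the protocol explains why. A responder rate is a reasonable thing to report; the objection is to testing biomarkers on it.

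**Conclusion.** The point holds in this limited form. As written, Aim c would test biomarkers on a yes/no response whose only definition is the CGI-I cut. In a sample of at most 50, that would usually cost useful power. Under the assumptions in step 4, the cost is about 8 to 28 points against a well-spread 7-point CGI-I. It would be about 13 to 31 points against a continuous outcome, but only if mitochondrial response would otherwise be cut. It is smaller for weak markers and can vanish if CGI-I ratings cluster.

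A reader might also infer that the trial's 80% power is in doubt. It is not on this ground: that figure is for the treatment comparison and reproduces at 79.9%. The change is worth making because it is cheap and concerns an item of the Primary Aim, not because the trial's main conclusion depends on it.

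**What to change.** In the Synopsis, Statistical Methods, replace the logistic regression for Aim c with full-scale models, and repeat them in section 6:

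- **CGI-I:** relate the biomarkers to the 7-point score in an ordinal (proportional-odds) or rank-based model that handles the two cross-over periods. The scale is rated at weeks 12 and 24, both times against baseline.
- **Mitochondrial function:** add a biomarker-by-treatment term to the mixed model already planned. Express the outcome as distance from normal, or change toward normal, and not as the raw value. State in advance the reference value that defines normal.
- **CGI-I responder rate by biomarker status:** keep it as a descriptive summary.

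No extra children, visits or samples are needed. The cost is a little more modelling work, including repeated measures for the ordinal model, and a headline that is a mean or ordinal shift instead of a responder odds ratio.

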## 1. ABSTRACT

Autism spectrum disorder (ASD) is a heterogeneous neurodevelopmental disorder often with life-long consequences that affects young children during critical developmental periods. The Centers for Disease Control estimates that ASD affects as many as 17 per 1000 children (1 in 59) in the United States suggesting that the prevalence is higher than previous estimates. Despite the dramatic rise in the detected prevalence of ASD over the past two decades, there is no effective medical treatment for core ASD symptoms (social communication and repetitive behavior), the closely associated problem of language impairment, or the underlying pathophysiology of ASD. Currently, the only accepted treatment for **core** ASD symptoms is behavior therapy, which may entail intensive one-on-one treatment over several years. Such therapy is inconsistently covered by medical insurance and may not be available in special education settings, thereby limiting its application. The *de facto* standard-of-care for treating ASD is a combination of educational and behavioral interventions.

Although interventions such as speech and occupational therapy may help modify neural pathways, they may not address the pathophysiology that underlies ASD. Despite these interventions, most children with ASD have incomplete recovery and need for long-term supportive care. Thus, a safe, effective and well-tolerated medical treatment that improves core and closely associated ASD symptoms, addresses the underlying physiology associated with ASD, and augments ongoing behavioral and educational interventions would have disease-modifying potential. To better understand if treatments commonly used in children with ASD are indeed normalizing physiological disturbances associated with ASD we aim to determine if a commonly used wide-spectrum nutritional supplement theoretically designed to normalize mitochondrial function does have the hypothesized effect of physiology in individuals with ASD.

The *primary aims* of this study are to evaluate the effect of a wide-spectrum nutritional supplement on mitochondrial function in individuals with ASD. Participants entered into the trial will have abnormalities in mitochondrial function that are associated with ASD (such abnormalities are found in approximately 50% of children with ASD) but are not diagnostic of mitochondrial disease. Specifically, children with mitochondrial disease (approximately 5% of the ASD population), which is a very severe disorder, will be excluded from the study so they can pursue more intensive appropriate treatment. As we believe 50% of children with ASD have some form of atypical variations in mitochondrial function, we will target these children to improve the function of their mitochondria. We hypothesizes that a nutritional supplement designed for children with ASD will have a physiological action of normalizing mitochondrial function and cellular physiology throughout the body. To test whether the targeted nutritional supplement is superior to placebo, we will study 50 children, between the ages of 2 years 6 months and 17 years 3 months, with confirmed ASD and known abnormal variations in mitochondrial at baseline. Participants will be randomly assigned to receive active treatment or placebo for 12-weeks under double-blind conditions and at the end of the 12 weeks switch to the opposite treatment arm. Mitochondrial function will be measured at baseline and after each treatment arm in order to determine if the supplement positively influences cellular biochemistry.

